## **Methodology:**

### **Study design**

Comparative study.

## **Patient Selection**

Inclusion criteria:

[figure not shown]
- Participants must be between 18 to 75 years old.
- More than 1- month post stroke patient.
- Participants must be able to walk with or without assistance.
- Patients including both the male and female.
- Participants must be able to provide informed consent to participate in the study.

Exclusion Criteria:

- Severe cognitive or communicative disorders.
- Significant joint malposition.
- Psychological, cognitive dysfunction, and any other neuromuscular problem.
- Pregnant women will be excluded to avoid any potential risks to the mother and fetus.
- Unstable cardiovascular disease like congenital heart disease, deep vein thrombosis, coronary heart disease, previous history of heart attack or heart failure.

## **Data collection procedure:**

Participants will be selected based on pre-determined inclusion criteria to ensure they fit for the study. Data will be collected through face-to-face interview using a pretested semi-structured questionnaire and informed verbal consent will be taken prior to interview. All the participants demographic information (age, weight, height, etc.) will be collected. Participants evaluated by Berg Balance test and Time Up & Go (TUG) test questionnaire form. All participant names have been properly defined to make sure confidentiality. After that the participants will be instructed to walk in their natural and comfortable manner. All participants will undergo a familiarization trial to get comfortable with the experimental setup and procedures. Then, participants will perform linear walking during two consecutive trials. Then take 2 minutes rest for treadmill walking after that again take 2 minutes rest for BWSTW. Data will be collected using a force plate and an 8-camera video monitoring system on all three walking modalities. The collected spatiotemporal data will be analyzed by statistical methods to identify differences among those modalities. Specific focus will be on key spatiotemporal parameters such as step length, stride length, cadence, gait speed, and the duration of the stance and swing phases use as important aspects of gait analysis

**Figure:** Flow chart of study plan

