### **Summary:**

This study aims to collect and analyze spatiotemporal data from stroke patients using an in-house gait analysis setup. Each walking modality-overground, self-paced treadmill, and body-weight supported treadmill provides distinct advantages and challenges. Overground walking simulates natural conditions but lacks mechanical support; self-paced treadmill walking provides a controlled environment with adjustable speed; and body-weight supported treadmill walking reduces lower extremity pressure and the risk of falling. A locally made body weight support structure (BWSS) is used for fall prevention in hemiparetic patients during data collection. The BWSS includes: Hand winch system with locking mechanism, Double pulley system, An overhead harness, and A 10 ft Stainless steel wire (loading capacity=5 ton). For Overground, data collection is done using two force plates positioned in the middle of a linear pathway, an 8-camera video monitoring system, and AcqKnowledge software is used for data analysis. Data collection from the self-paced treadmill and body-weight supported treadmill also occur through the video monitoring system. Data collection will adhere to standard protocols to ensure safety and accuracy. Participants will walk along the pathway, and gait data will be recorded using the force plates and video system. By analyzing gait parameters such as step length, stride length, cadence, gait speed, and the duration of stance and swing phases, the study aims to identify which modality offers the most consistent and stable gait patterns, indicating improved motor control and coordination.

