### **Objectives:**

In this study, we aim to evaluate the gait differences among three different walking modalities with respect to spatiotemporal gait parameters. This will be achieved through a comparative analysis of spatiotemporal data between those groups. To ensure the safety of the subjects, the data collection protocols will be strictly followed, incorporating already tested procedures that have shown no probable risk. The BWSS has been tested with healthy individuals and is manufactured using widely available components in Bangladesh. The objectives of the study are as follows:

- **Study objectives:** To evaluate the variations in spatiotemporal gait parameters of three different walking modalities and analyze and determine which walking technique provides the most reliable gait metrics, suggesting a more stable and possibly advantageous recovery outcome.
- **Study Hypothesis:** We hypothesize that body weight supported treadmill walking will exhibit the least variability in spatiotemporal gait parameters compared to overground walking and self-paced treadmill walking. This suggests that BWST provides a more controlled environment, promoting more consistent and reliable gait patterns, which may translate to a more stable and potentially advantageous recovery outcome for individuals with stroke.

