**Table 1: Summary of the comparative study between healthy and post stroke individuals**

Aspect of the study	Description
Study Type	Comparative
Design	Comparative study
No of subjects	25
Objective	Evaluate the variations in spatiotemporal gait parameters of those
waking modalities.	
Study Population	Inclusion Criteria for post-stroke patients:

	
 
Participants must be between 18 to 75 years old.
 
More than 1- month post stroke.
 
Participants must be able to walk with or without assistance.
 
Patients including both the male and female.
 
Participants must be able to provide informed consent to participate in the study.
 
 
Exclusion Criteria for post-stroke patients:
 
 
Severe cognitive or communicative disorders.
 
Significant joint malposition.
 
Psychological, cognitive dysfunction, and any other neuromuscular problem.
 
Pregnant women will be excluded to avoid any potential risks to the mother and fetus.
 
Unstable cardiovascular disease
 

Procedure	
Post stroke group:
 
 
Giving instruction
 
Randomly assigning patients to all the modalities
 
Data collection through force plate and video cameras
 
Extracted spatiotemporal parameters from recorded data
 

Outcomes	
Primary Outcome:
 
 
Gait velocity
 
 
Secondary Outcome:
 
 
Step length
 
Stride length
 
Cadence
 
Stance and swing phases duration
 
Single and double support time
 
Ground reaction force
 

Data Collection	
Data collected before trial:
 
 
Patient clinical condition
 
Time after stroke and before data collection
 
Duration of therapy/rehabilitation
 
 
Data collected during walking:
 
 
Force plate data
 
Video monitoring data
 

Data analysis	
 
Comparative test between the primary outcome of three group
 
Wilcoxon sign rank test & a paired sample t test
 
Interclass correlation coefficient between those group
 
Mean difference and standard deviation between those group
 

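### The procedure text walks every participant through one fixed order ending in body-weight supported treadmill walking, while Table 1 says assignment is random; under a fixed order, modality cannot be separated from position

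*Protocol*

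**What the plan says.** The Protocol, under Data collection procedure, first gives a general run-in: "All participants will undergo a familiarization trial to get comfortable with the experimental setup and procedures". The measured walking follows in sequence: "Then, participants will perform linear walking during two consecutive trials", and next "Then take 2 minutes rest for treadmill walking after that again take 2 minutes rest for BWSTW". The Summary ties the linear pathway to overground walking ("For Overground, data collection is done using two force plates positioned in the middle of a linear pathway"), so the sequence reads overground, treadmill, body-weight supported treadmill (BWST). Nothing in that section mentions varying the order.

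Table 1, in its Procedure row, lists "Randomly assigning patients to all the modalities". It does not say whether this means a random order or random groups.

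Two other statements show that each person supplies data on every modality. The procedure section says "Data will be collected using a force plate and an 8-camera video monitoring system on all three walking modalities", and the Data analysis row of Table 1 names a Wilcoxon signed rank test and "a paired sample t test".

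The hypothesis under Objectives is that "body weight supported treadmill walking will exhibit the least variability in spatiotemporal gait parameters" compared with the other two modalities.

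**The concern.** In a within-participant comparison, the order in which conditions are walked is part of the design. Practice, growing confidence in the laboratory and fatigue can all change gait over a session. If everyone walks in the same order, each difference between modalities also contains the difference between the positions they occupy.

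This bears directly on the study's main claim, because BWST would always come last. Practice and fatigue can act in opposite directions, so a position effect could either mimic or hide the hypothesised advantage. It cannot be left to the analysis stage: once all participants have walked one sequence, the data hold no information for separating the two effects. A reader relying on Table 1 would assume that order had been randomised and that this problem was absent.

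**Working it through.** **Step 1: set the passages side by side.**

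| Reading of the Table 1 step | What it conflicts with |
|---|---|
| Random order of the three modalities | The single sequence in Data collection procedure |
| Random allocation to one modality each | Data on all three modalities (same section) and the paired tests (Table 1) |

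The texts conflict on either reading, and no text in the copy at hand reconciles them.

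**Step 2: is modality estimable under the fixed sequence?** Take n = 25 participants with three walks each, 75 rows in all. The model has 25 participant columns, 2 position contrasts and 2 modality contrasts: 25 + 2 + 2 = 29 columns.

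| Order scheme | Rank (of 29) |
|---|---|
| One common order | 27 |
| All six orders | 29 |
| Three-sequence Latin square | 29 |

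With one order, overground is always position 1, treadmill position 2 and BWST position 3. The two modality columns are identical to the two position columns, so two ranks are lost (29 − 27 = 2). This needs no assumption about how large a position effect is.

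**Step 3: illustrate the consequence for mean velocity, the primary outcome.** The plan gives no figure for a position effect. Its own sample size inputs (difference 0.17, SD 0.3, k = 3, 80% power, two-sided 5%) give

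N = 2 × 0.3² × (0.842 + 1.960)² / (0.17² × 2) = 24.4,

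which agrees with the stated 24, raised to 25 for dropout.

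Inputs for the illustration:
- n = 25, from the Protocol.
- SD of the paired difference 0.30, assumed. The Protocol does not say what its SD of 0.3 refers to.
- Drift per position 0.005 to 0.05 m/s, assumed and linear.
- No true modality effect.

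The bias is 2 × drift for BWST versus overground (two positions apart) and 1 × drift for adjacent modalities. The paired t test has 24 degrees of freedom and noncentrality bias / (SD/√25). At a drift of 0.05 this is 0.10 / 0.06 = 1.67 for BWST versus overground. Rejection rates at two-sided 5%:

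| Drift (m/s per position) | BWST v overground | Adjacent modalities |
|---|---|---|
| 0.005 | 0.053 | 0.051 |
| 0.01 | 0.062 | 0.053 |
| 0.02 | 0.098 | 0.062 |
| 0.05 | 0.360 | 0.126 |

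**Step 4: sensitivity to the SD.** If 0.3 is instead the SD of a single measurement, the SD of differences is 0.3 × √(2(1 − r)), where r is the within-participant correlation. For BWST versus overground, over the same drift range:
- r = 0 (SD 0.42): about 5% to 20%.
- r = 0.8 (SD 0.19): about 6% to 72%.

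**Step 5: does balancing work?** A simulation of 40,000 runs (n = 24, SD 0.30, drift 0.005, 0.02 and 0.05, unadjusted paired t test) gave rejection rates of 0.049, 0.047 and 0.045 with six orders, and 0.050, 0.047 and 0.045 with a Latin square. With 24 participants the mean position difference between BWST and overground is 0. A 25th participant makes it at most 2/25 = 0.08 positions, or 0.08 × 0.05 = 0.004 m/s at the largest drift. The simulation covers linear drift only, without carry-over from one modality to the next.

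**The case against.** The strongest reply is that only a wording conflict is established. The sample size section presents Table 1 as the summary of the study's aspects, and Table 1 has an explicit random step. On that view the procedure text merely lists the modalities and rests in loose prose, and the bias never arises. The flow chart, which is not in the copy at hand, might confirm this. It is a fair point that the aliasing is conditional. But the procedure text is plainly sequential, and no flow chart could make both texts true.

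A second reply is that the random wording may be left over from a parallel-group template, since the sample size section speaks of groups and equal allocation. That may explain how the conflict arose. It does not remove it, because the tests are paired and each person walks all three modalities.

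Third, the drift and the SD of differences are assumed, and the error rates concern mean velocity whereas the hypothesis concerns variability. This stands. The rates are illustrative, they vary widely with the assumed SD, and at the smallest drift they are practically nil. The case does not rest on them.

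Fourth, the familiarization trial and the rests may dampen position effects. They may, but they cannot show that none remains.

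Finally, the case report form has no field for order, but it has no field for modality either, so its silence says little about which rule was intended. This also stands; the form matters only for the remedy.

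**Conclusion.** The concern holds. It is certain that Data collection procedure and Table 1 contradict each other on how participants meet the three modalities. If the procedure text governs, both modality contrasts are exactly aliased with position (rank 27 against 29), whatever the size of any position effect, and no analysis can undo this. If Table 1 governs and means random order, systematic position bias does not arise and only the procedure text needs correcting.

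The size and direction of the bias cannot be determined from the documents, and no size is offered for variability. For mean velocity, the false-positive rate of about 5% to 36% for BWST versus overground rests on an assumed SD of differences of 0.30 and an assumed linear drift of 0.005 to 0.05 m/s per position. This should be fixed before data collection.

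**What to change.** State one order rule, in the same terms, in Data collection procedure, Table 1 and, if it shows an order, the flow chart.

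**Preferred.** Randomise each participant to an order of the three modalities from a position-balanced set, and add a case-report-form field for the order actually walked. Either the six possible orders or a three-sequence Latin square balances position. The six orders are better because each modality then follows each other modality equally often; the Latin square contains only three of the six ordered neighbour pairs.

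**If the order must stay fixed.** Delete the random-assignment step from Table 1 and state that differences between modalities cannot be separated from order effects.

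**Cost.** The preferred change needs a short randomisation list, one form field and two sentences; the sample size is unchanged. Its small downside is that set-up changes between modalities will differ by participant. The fallback costs only wording but leaves the aliasing in place.

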### Phase-3-Extended Study (0):

The aim of this phase of study is to compare the Spatiotemporal parameter among different waking modalities. The standard protocols will be followed while conducting experiment, in the Department of Biomedical Engineering (BME), BUET. The various aspect of this final and most important component of the study are described below:

**Sample Size calculation:** In this comparative study, the gait velocity in between different waking modalities is considered as the primary parameters. The following formula may use for calculating the sample size for each group of the trial:

$$\text{Sample size, } N = \frac{2\sigma^2(Z_{1-\beta} + Z_{1-\alpha/2})^2}{d^2(k-1)} \quad \dots \dots \dots \quad (i)$$

Where,

N = Required sample size

$d$  = Difference in means of two group (effect size)

$$\sigma = \text{SD}$$

**k** = is the number of groups being compared.

$Z_{1-\beta}$  = It is the desired power

$Z_{1-\alpha/2}$  = Critical value and a standard value for the corresponding level of confidence. (At 95% CI it is 1.96)

To estimate the sample size, we considered the mean difference of the velocity of the post stroke patient to be at least 0.17 with a standard deviation of 0.3. We estimated that 24 individuals would be needed to satisfy the comparative studies between three groups, based on the statistical power of 80%, at a two-sided alpha level of 0.05. The statistical formula (i) used for the comparative test [10]. Considering dropouts and left-against-medical advice (LAMA) cases, sample size  $N = 25$  will be considered. Thus, a total of 25 subjects will be considered for the equal allocation of this study. The different aspects of the study are summarized in Table I.

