### **Introduction:**

Stroke is the leading cause of disability worldwide, affecting the lives of millions of people. One of the most debilitating effects of stroke is impaired gait, which impairs mobility and independence [1]. It is especially prevalent in low- and middle-income countries such as Bangladesh. Stroke is the third leading cause of death from non-communicable diseases in Bangladesh, putting a significant burden on both individuals and the healthcare system. Stroke prevalence in Bangladesh is around 11.39 per thousand people, with higher rates in rural areas and among elderly males [2]. Gait abnormalities are experienced by about 80% of stroke survivors, and they can significantly impair their daily activities and overall quality of life [3]. The significant number of disability-adjusted life years (485 per 10,000 people) lost due to stroke severely impacts the nation's economy [4]. Despite the high occurrence of disability due to stroke in Bangladesh, there are significant limitations in analyzing the gait characteristics of stroke patients. Gait rehabilitation uses a variety of walking modalities, such as body weight supported treadmill walking, self-paced treadmill walking, and overground walking. Every modality has particular benefits and drawbacks. The most natural kind of gait training is provided by walking on terrain that closely resembles actual walking conditions. However, because of the unpredictable nature of the environment and the lack of

mechanical support, it can be challenging for stroke patients [5]. Self-paced treadmill walking provides a controlled environment in which the patient's speed can be adjusted based on their abilities, allowing for a consistent walking rhythm and feedback [6]. This modality is useful for strengthening gait patterns and increasing endurance. However, body weight supported treadmill walking allows the patient to partially offload their weight, which lessens the pressure on their lower extremities and improves safety by lowering the chance of falls [7]. Variability in gait parameters such as step length, stride length, cadence, gait speed, and the duration of the stance and swing phases is an important aspect of gait analysis. High variability in gait frequently indicates instability and inefficiency, which are undesirable outcomes in rehabilitation. Lower variability, on the other hand, indicates more consistent and stable gait patterns, implying improved motor control and coordination.

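### The primary outcome and sample size rest on mean gait velocity although the hypothesis concerns variability, and on a treadmill, above all the body-weight supported one, that mean may be a set belt speed

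*Protocol*

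**What the plan says.** **Primary outcome and sample size.** In the Protocol, Annexure C, under Phase-3-Extended Study, the sample-size paragraph states that "the gait velocity in between different waking modalities is considered as the primary parameters". It assumes a "mean difference of the velocity of the post stroke patient to be at least 0.17 with a standard deviation of 0.3", "based on the statistical power of 80%, at a two-sided alpha level of 0.05". Its result is 24, raised to 25 for dropouts. Table 1 names gait velocity as the sole primary outcome. Step length, stride length, cadence, phase durations, support times and ground reaction force are secondary. Table 1 names no variability measure as an outcome.

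**Hypothesis and aims.** Under Objectives, the hypothesis is that "body weight supported treadmill walking will exhibit the least variability in spatiotemporal gait parameters". The Annexure B responses to items 1 and 2 give variability of spatiotemporal parameters as the primary aim. The Rationale presents the study as an investigation of variability across the three environments.

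**Treadmill speed.** The Summary says that "self-paced treadmill walking provides a controlled environment with adjustable speed". The Introduction says that "the patient's speed can be adjusted based on their abilities". Neither says whether the patient, an automatic controller or an operator makes the adjustment. For the body-weight supported treadmill the text describes offloading and safety, but not how speed is set. The Data collection procedure asks participants to walk naturally and comfortably and gives no rule for belt speed. The Case Report Form has one walking-speed field and none for modality, belt speed or control mode.

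**The concern.** There are two linked problems.

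First, the question and the primary outcome differ. The hypothesis ranks three walking conditions by consistency of gait. The primary comparison ranks them by average speed. A patient can walk slowly and steadily, or fast and steadily, so a difference in mean speed carries no information about consistency. The study could meet its primary outcome and leave its hypothesis untested.

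Second, mean velocity need not be a response of the patient on a treadmill. If someone other than the patient sets the belt, the velocity recorded there is an input to the experiment. A significant difference between overground and supported treadmill walking could then show only that the belt was run slower or faster than the patient's overground pace. If nobody records how the belt was controlled, no later analysis can separate the two explanations.

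**Working it through.** **1. The plan's own figure.** Inputs from the sample-size paragraph: SD 0.3, difference 0.17, k = 3 modalities, 80% power, two-sided alpha 0.05. No unit is given there; the Case Report Form records walking speed in m/s.

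N = 2 × SD² × (z for power + z for alpha)² / (d² × (k − 1))

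= 2 × 0.09 × (0.8416 + 1.9600)² / (0.0289 × 2) = 1.4128 / 0.0578 = 24.44.

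This agrees with the stated 24, and with 25 when rounded up. With k = 3 the factor 2/(k − 1) is 1, so the formula coincides with the normal approximation for a paired comparison whose SD of differences is 0.3. The arithmetic is not in dispute. It sizes the study for a difference in mean velocity.

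**2. Outcome against hypothesis.**

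| Place in the Protocol | Quantity |
|---|---|
| Annexure B, items 1 and 2 | variability of gait parameters |
| Objectives, hypothesis | least variability under body-weight support |
| Rationale | variability across environments |
| Sample-size paragraph | difference in mean velocity, 0.17 |
| Table 1, primary outcome | gait velocity |
| Table 1, analysis | paired t test, Wilcoxon signed-rank test |

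A paired test on one mean velocity per patient and modality compares locations. It does not compare spread between strides.

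**3. Velocity and belt speed.** For a walk of duration T, mean walking velocity relative to the belt = mean belt speed + (net change of position on the treadmill)/T. The net change cannot exceed the length of the belt, so over a sustained walk the second term is close to zero and mean velocity equals mean belt speed. This is geometry and needs no outside source.

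For a single stride on a belt held at constant speed b: stride velocity = b + (drift during the stride)/(stride time). Only drift can vary. Velocity variability is therefore mechanically constrained, though not zero. In the same way, stride length = b × stride time + drift, so stride-level measures are partly tied together on a constant belt.

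**4. Illustration of size.** Assumptions, none of them stated in the Protocol: the belt alone shifts mean velocity from overground by a given offset; the SD of paired differences is 0.3 or 0.2; n = 25; two-sided paired t test at 0.05. The noncentrality is offset × √25 / SD, for example 0.17 × 5 / 0.3 = 2.83.

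| Assumed offset | Probability significant, SD 0.3 | Probability significant, SD 0.2 |
|---|---|---|
| 0.05 | 0.13 | 0.23 |
| 0.10 | 0.36 | 0.67 |
| 0.17 | 0.78 | 0.98 |

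These are the ordinary power of the test for a shift of that size, whatever its cause. They show that the test cannot tell a belt offset from an effect on gait. They do not show that an offset will occur.

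**The case against.** **One treadmill is called self-paced throughout.** The name is in the title, the aims and the hypothesis, and the study cited for that modality compares self-paced with fixed-speed treadmill walking. Participants are told to walk naturally and comfortably. If the belt follows the patient, its speed is the patient's chosen pace and velocity is a genuine gait measure. This stands. A reader might infer that velocity is a machine setting on both treadmills; the documents do not support that. The gap is clear for the supported treadmill and is only an ambiguity for the self-paced one. The flow chart is also not visible, so the absence of set-up detail should be read with some care.

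**The hypothesis is not true by construction.** A reader might infer that it is, because velocity cannot vary on a constant belt. No part of the Protocol says that a belt is constant, the walker can drift, and the hypothesis covers spatiotemporal parameters in general. The point is conditional: if the supported belt is held constant, the constraint on velocity variability works in the hypothesis's favour.

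**The 0.78 is not a predicted false-positive rate.** It restates the power for an assumed offset equal to the planning difference. The Protocol also does not say that 0.3 is an SD of paired differences. This stands.

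**The Objectives also speak more broadly of gait differences among modalities.** Mean velocity is a fair descriptor for that aim. But the only stated hypothesis concerns variability, and the primary outcome does not address it.

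**Recording belt control might be enough.** That would settle what a velocity difference means. It would not make mean velocity a test of variability.

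**Conclusion.** The concern holds in this form: the primary outcome and sample size address mean velocity, while the hypothesis and stated aims address variability, so the primary test does not answer the study's question. This part follows from the text alone and needs no assumption about the equipment.

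The belt-speed part is conditional. It applies to any treadmill walk in which the patient does not control the belt. The Protocol leaves this undescribed for the supported treadmill and unclear for the self-paced one. Its size cannot be fixed from the document: across the assumed offsets of 0.05 to 0.17 and SDs of differences of 0.3 or 0.2, the probability of a significant difference due to the belt runs from 0.13 to 0.98. The planned sample size is correctly computed for velocity, but it says nothing about the power to compare variability.

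**What to change.** 1. In the sample-size paragraph and Table 1, name as primary a within-person variability measure that matches the hypothesis. One example is the coefficient of variation of stride time, taken from the video that is recorded in all three modalities. Keep gait velocity as a secondary outcome.
2. Restate the sample-size paragraph: either say plainly that 25 was planned for a difference in velocity, or recalculate for the new outcome. The Protocol gives no mean or SD for a variability measure, so no replacement number can be offered here.
3. Describe how belt speed is controlled on each treadmill, and record belt speed and control mode (patient or operator) for every treadmill walk.
4. State that velocity is not interpreted as an effect on gait where an operator sets the belt.

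**Cost.** Items 3 and 4 need a few sentences and a few fields. Item 1 costs more than a change of wording. The Case Report Form holds single values for speed and cadence, and one value per leg for stride and step length, so it needs entries per modality and at stride level. Overground walking consists of two trials, and the number of strides may limit the precision of a coefficient of variation; the strides available per modality should be checked first. Stride-level measures are also partly constrained on a constant belt, which is a further reason to record control mode.

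### The stated 80% power with 24 patients is not established: formula (i) does not fit the paired design, the SD of 0.3 is undefined, and the dropout patient only restores the rounding

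*Protocol*

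**What the plan says.** The Sample Size calculation (protocol, Phase-3-Extended Study) makes gait velocity the primary parameter and offers formula (i) for "calculating the sample size for each group of the trial": N = 2σ²(Z₁₋β + Z₁₋α/2)² / [d²(k−1)]. Here d is the difference between two group means, k is the number of groups, and σ is glossed only as SD.

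The inputs are a "mean difference of the velocity of the post stroke patient to be at least 0.17 with a standard deviation of 0.3", with 80% power and two-sided alpha 0.05. The stated result is: "We estimated that 24 individuals would be needed to satisfy the comparative studies between three groups, based on the statistical power of 80" per cent. The number is then raised to 25, with the reason given as "Considering dropouts and left-against-medical advice (LAMA) cases". No loss rate is stated. The paragraph concludes that "a total of 25 subjects will be considered for the equal allocation of this study".

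Elsewhere the protocol describes a single group. The Data collection procedure has the same participants walk overground, then on the treadmill, then with body-weight support: "Data will be collected using a force plate and an 8-camera video monitoring system on all three walking modalities". Table 1 lists "Randomly assigning patients to all the modalities" under Procedure. Under Data analysis it lists a Wilcoxon signed-rank test and "a paired sample t test".

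**The concern.** The sample-size paragraph is written for separate groups with equal allocation, while the procedure and tests are for one group measured three times. In a paired comparison the power depends on the SD of the within-patient differences. The formula has no within-patient term, and the text does not say whether 0.3 is that SD or the SD of velocity within one modality.

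The divisor (k−1) is also odd. For a fixed difference between two means, it makes the required number fall as more groups are compared. A source is cited for the formula, but the text does not explain the divisor.

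This paragraph is the only justification for enrolling 25 patients. If the 80% is accepted as it stands, a non-significant velocity contrast could be read as coming from an adequately powered study when that has not been shown.

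**Working it through.** **Inputs, all from the Sample Size calculation:** d = 0.17, SD = 0.3, k = 3, two-sided alpha 0.05 (z = 1.960), power 80% (z = 0.8416). The squared sum of the z values is (1.960 + 0.8416)² = 7.849.

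**1. The plan's own figure.** Formula (i): 2 × 0.09 × 7.849 / (0.0289 × 2) = 24.44 (24.42 with z rounded to 1.96 and 0.84). The stated 24 is this result rounded down; rounded up it is 25. The formula's own power at 24 is Φ(√24 × 0.17/0.3 − 1.96) = Φ(0.816) = 79.3%; at 25 it is 80.9%.

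**2. The divisor.** The same inputs give 48.89 at k = 2, 24.44 at k = 3 and 5.43 at k = 10. Without the divisor, the usual formula for two independent means needs 49 per group, and 24 per group would have about 50% power.

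**3. Link to the paired design.** The normal-approximation paired formula is N = SD_d²(z₁₋α/2 + z₁₋β)²/d², where SD_d is the SD of within-patient differences. With SD_d = 0.3 it gives 0.09 × 7.849/0.0289 = 24.44. It matches formula (i) because k−1 = 2 cancels the leading 2 when k = 3, and only if 0.3 is SD_d.

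**4. Reading A: 0.3 is the SD of differences.** Noncentral-t power for a two-sided paired t test, difference 0.17:

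| Completers | Power |
|---|---|
| 24 | 75.8% |
| 25 | 77.6% |
| 26 | 79.3% |
| 27 | 80.9% |

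So 27 completers are needed for 80%. The difference detectable with 80% power is 0.175 with 25 and 0.179 with 24. If SD_d were 0.29, 25 completers would give 80.3%.

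**5. Reading B: 0.3 is the per-modality SD.** Then SD_d = 0.3 × √(2(1−ρ)). The protocol gives no within-patient correlation ρ, so the values below are assumptions.

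| ρ (assumed) | SD_d | Power with 25 | N for 80% |
|---|---|---|---|
| 0 | 0.424 | 49% | 51 |
| 0.3 | 0.355 | 63% | 37 |
| 0.5 | 0.300 | 78% | 27 |
| 0.6 | 0.268 | 86% | 22 |
| 0.8 | 0.190 | 99% | 12 |

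Power with 25 reaches 80% at ρ of about 0.53 (SD_d 0.291).

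**6. Dropout.** Rounded up, formula (i) needs 25 and 25 are enrolled, so the allowance is 25 − 25 = 0. Even if 24 were the need, one patient in 25 covers a loss of 4%.

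**7. Which contrast.** Three modalities give three pairwise comparisons, and the text does not say which the power refers to. If it were meant to cover all three with alpha split (assumed 0.05/3) and SD_d 0.3, power with 25 would be 61% and 36 would be needed.

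**The case against.** The strongest reply is that 0.3 can naturally be read as the SD belonging to the mean difference in the same sentence. Formula (i) then equals the paired normal-approximation formula at the only k used here, and the shortfall is small: 77.6% against 80% with 25, or a detectable difference of 0.175 against 0.17. Much of that gap comes from using z instead of the t distribution, a common planning shortcut. Rounding 24.44 down costs 0.7 percentage points on the formula's own terms. Talk of groups and equal allocation may be loose wording for 25 observations per modality. The split-alpha case is not in the protocol, and multiplicity is often left to an analysis plan. All three walks also appear to take place in one session, so loss may be low.

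Much of this is fair. The study is not shown to be underpowered: on the per-modality reading with a correlation of 0.6 or more, 25 patients exceed 80% for a single contrast. The split-alpha figure should add no weight beyond asking which contrast is meant.

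Three points remain. The SD is still undefined, and the answer turns on it. The agreement with the paired formula is neither stated nor general. The extra patient is not a dropout margin, although Annexure B (item 3) ends a trial on discomfort, fatigue or deterioration, so incomplete sets of three walks are foreseeable.

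**Conclusion.** The concern holds, as a failure to establish 80% power and not as proof of low power. With 25 completers, a difference of 0.17 and two-sided 0.05 for one paired contrast, power reaches 80% only if the SD of within-patient differences is at most about 0.29. That condition covers both readings, since a per-modality SD of 0.3 meets it when the correlation is about 0.53 or higher. If the SD of differences is 0.3, power is 77.6%, falling to 75.8% once one patient is lost. If 0.3 is the per-modality SD, the range is 49% to 99% over the correlations assumed here. The claim that 25 includes cover for dropout is wrong on the formula's own result. The paragraph should be corrected.

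**What to change.** Keep 25 enrolled and rewrite the Sample Size paragraph:

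- Replace formula (i) with the paired-difference calculation, and drop the wording about each group and equal allocation.
- State whether 0.3 is the SD of within-patient differences or the per-modality SD; if the latter, give the assumed correlation.
- Name the pairwise contrast and the alpha that the power covers. If all three contrasts under a split alpha are meant, say so and restate the power.
- If the formula's result is still reported, give it as 25, not 24.
- Remove the statement that 25 allows for dropout. If an allowance is wanted, state a rate and divide by (1 − rate); from a need of 25, assumed rates of 5%, 10% and 20% give 27, 28 and 32.
- State the power conditionally, for example: with 25 completers, power is 80% for a difference of 0.17 at two-sided 0.05 per contrast only if the SD of within-patient differences is at most 0.29; with an SD of 0.30 it is 78%, or the detectable difference is 0.175; with 24 completers these become 76% and 0.179.

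The cost is one rewritten paragraph. Enrolment and the travel budget for 25 participants stay as they are unless the sponsor chooses to add a dropout allowance. The stated power may read slightly less favourably than 80%.
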